## Appendix 8 Reference ranges of laboratory parameters

Analyte No.	Analyt	Test Group	Synonym	Sex	>= Age	< Age	Unit	Lower Limit	Upper Limit	Unit	Spezimen	Method (Analyzer)
101	Potassium	Elektrolyte	K	Unisex			year	3,5	5,1	mmol/L	Serum	ISE indirect (cobas c501/Integra 400 Plus)
100	Sodium	Elektrolyte	SODIUM	Unisex			year	136	145	mmol/L	Serum	ISE indirect (cobas c501/Integra 400 Plus)
111	Alanine Aminotransferase	Enzyme	ALT	Male			year	5	50	U/L	Serum	PHO (cobas c501/Integra 400 Plus)
113	Alkaline Phosphatase	Enzyme	ALP	Male			year	40	129	U/L	Serum	PHO (cobas c501/Integra 400 Plus)
110	Aspartate Aminotransferase	Enzyme	AST	Male			year	5	50	U/L	Serum	PHO (cobas c501/Integra 400 Plus)
241	Creatine Kinase	Enzyme	CK	Male			year	7	308	U/L	Serum	PHO (cobas c501/Integra 400 Plus)
600	Creatine Kinase MB	Enzyme	CKMB	Unisex			year	3,0	25,0	U/L	Serum	PHO (cobas c501/Integra 400 Plus)
112	Gamma Glutamyl Transferase	Enzyme	GGT	Male			year	3	71	U/L	Serum	PHO (cobas c501/Integra 400 Plus)
343	Ery. Mean Corpuscu. Hemoglobin	Hematology	MCH	Unisex			year	1,600	2,000	fmoI	EDTA	Calculation by formula (Sysmex XN-1000)
344	Ery. Mean Corpuscular Volume	Hematology	MCV	Male			year	79,0	92,2	fL	EDTA	Calculation by formula (Sysmex XN-1000)
347	Erythrocytes	Hematology	RBC	Male			year	4,63	6,08	T/L	EDTA	DC sheath flow detection method (Sysmex XN-1000)
345	Hematocrit	Hematology	HCT	Male			year	0,401	0,510	L/L	EDTA	Cumulative pulse height method (Sysmex XN-1000)
346	Hemoglobin	Hematology	HGB	Male			year	8,50	10,86	mmol/L	EDTA	SLS detection method (Sysmex XN-1000)
348	Leukocytes	Hematology	WBC	Male			year	4,23	9,07	G/L	EDTA	Fluorescence flow cytometry (Sysmex XN-1000)
341	Platelets	Hematology	PLAT	Male			year	163	337	G/L	EDTA	DC sheath flow detection method (Sysmex XN-1000)
529	Reticulocytes	Hematology	RETI	Male			year	26,0	95,0	G/L	EDTA	Fluorescence flow cytometry (Sysmex XN-1000)
523	Basophils/Leukocytes	Hematology %	BASOLE	Male			year	0,2	1,2	%	EDTA	Calculation by formula (Sysmex XN-1000)
522	Eosinophils/Leukocytes	Hematology %	EOSLE	Male			year	0,8	7,0	%	EDTA	Calculation by formula (Sysmex XN-1000)
520	Lymphocytes/Leukocytes	Hematology %	LYMLE	Male			year	21,8	53,1	%	EDTA	Calculation by formula (Sysmex XN-1000)
521	Monocytes/Leukocytes	Hematology %	MONOLE	Male			year	6,0	15,1	%	EDTA	Calculation by formula (Sysmex XN-1000)
349	Neutrophils/Leukocytes	Hematology %	NEUTLE	Male			year	34	67,9	%	EDTA	Calculation by formula (Sysmex XN-1000)
340	Reticulocytes/Erythrocytes	Hematology %	RETIRBC	Male			year	0,51	1,81	%	EDTA	Calculation by formula (Sysmex XN-1000)
707	Hepatitis B Virus Core AB	Serology	HBCAB	Unisex			year	neg	neg		Serum	ECLIA (cobas e601/cobas e411)
702	Hepatitis B Virus Surface AG	Serology	HBSAG	Unisex			year	neg	neg		Serum	ECLIA (cobas e601/cobas e411)
704	Hepatitis C Virus AB	Serology	HCAB	Unisex			year	neg	neg		Serum	ECLIA (cobas e601/cobas e411)
700	HIV-1/2 Antibody/HIV-1 p24 AG	Serology	HIV12P24	Unisex			year	neg	neg		Serum	ECLIA (cobas e601/cobas e411)
477	Troponin I	Special Tests	TROPONI	Unisex			year	neg	neg		Serum	Stick Mölab (manual)
121	Creatine Kinase MB/CK	Calculated Parameter	CKMBCK	Unisex			year	0	6	%	Serum	Calculation by formula
166	Blood Urea Nitrogen	Substrate	UREAN	Unisex	18	60	year	2,14	7,14	mmol/L	Serum	PHO (cobas c501/Integra 400 Plus)
166	Blood Urea Nitrogen	Substrate	UREAN	Unisex	61	90	year	2,86	8,21	mmol/L	Serum	PHO (cobas c501/Integra 400 Plus)
171	Bilirubin	Substrate	BILI	Unisex			year	0,0	21,0	µmol/L	Serum	PHO (cobas c501/Integra 400 Plus)
139	Calcium	Substrate	CA	Unisex	61	90	year	2,20	2,55	mmol/L	Serum	PHO (cobas c501/Integra 400 Plus)
139	Calcium	Substrate	CA	Unisex	18	60	year	2,15	2,50	mmol/L	Serum	PHO (cobas c501/Integra 400 Plus)
156	Cholesterol	Substrate	CHOL	Unisex			year	0,0	5,2	mmol/L	Serum	PHO (cobas c501/Integra 400 Plus)
146	Creatinine	Substrate	CREAT	Male			year	59	104	µmol/L	Serum	PHO (cobas c501/Integra 400 Plus)
167	Direct Bilirubin	Substrate	BILDIR	Unisex			year	0,0	5,0	µmol/L	Serum	PHO (cobas c501/Integra 400 Plus)
143	Glucose	Substrate	GLUC	Unisex			year	4,11	5,89	mmol/L	Serum	PHO (cobas c501/Integra 400 Plus)
154	Protein	Substrate	PROT	Unisex			year	64	83	g/L	Serum	PHO (cobas c501/Integra 400 Plus)

155	Triglycerides	Substrate	TRIG	Unisex		year	0,0	2,3	mmol/L	Serum	PHO (cobas c501/Integra 400 Plus)
147	Urate	Substrate	URATE	Male		year	202,3	416,5	µmol/L	Serum	PHO (cobas c501/Integra 400 Plus)
383	Amphetamine	Urine Drug Sticks	AMPHET	Unisex		year	neg	neg		Spot Urine	Cassette SureStep (manual)
387	Barbiturates	Urine Drug Sticks	BARB	Unisex		year	neg	neg		Spot Urine	Cassette SureStep (manual)
388	Benzodiazepines	Urine Drug Sticks	BNZDZPN	Unisex		year	neg	neg		Spot Urine	Cassette SureStep (manual)
382	Cannabinoids	Urine Drug Sticks	CANNAB	Unisex		year	neg	neg		Spot Urine	Cassette SureStep (manual)
389	Cocaine	Urine Drug Sticks	COCAINE	Unisex		year	neg	neg		Spot Urine	Cassette SureStep (manual)
381	Cotinine	Urine Drug Sticks	COTININE	Unisex		year	neg	neg		Spot Urine	Stick Nal von Minden (manual)
390	Methadone	Urine Drug Sticks	METHDN	Unisex		year	neg	neg		Spot Urine	Cassette SureStep (manual)
384	Methamphetamine	Urine Drug Sticks	METHAMPH	Unisex		year	neg	neg		Spot Urine	Cassette SureStep (manual)
385	Methylenedioxyamphetamin	Urine Drug Sticks	MDMA	Unisex		year	neg	neg		Spot Urine	Cassette SureStep (manual)
391	Opiate	Urine Drug Sticks	OPIATE	Unisex		year	neg	neg		Spot Urine	Cassette SureStep (manual)
386	Tricyclic Antidepressants	Urine Drug Sticks	TRCYANDP	Unisex		year	neg	neg		Spot Urine	Cassette SureStep (manual)
366	Bacteria	Urine Sediment	BACT	Unisex		year	0	0	1/HPF	Spot Urine Sediment	Microscopy (manual)
365	Calcium Oxalate Crystals	Urine Sediment	CYCAOXA	Unisex		year	0	0	1/HPF	Spot Urine Sediment	Microscopy (manual)
362	Erythrocytes	Urine Sediment	RBC	Unisex		year	0	2	1/HPF	Spot Urine Sediment	Microscopy (manual)
378	Granular Casts	Urine Sediment	CSGRAN	Unisex		year	0	0	1/HPF	Spot Urine Sediment	Microscopy (manual)
364	Hyaline Casts	Urine Sediment	CSHYAL	Unisex		year	0	0	1/HPF	Spot Urine Sediment	Microscopy (manual)
361	Leukocytes	Urine Sediment	WBC	Unisex		year	0	5	1/HPF	Spot Urine Sediment	Microscopy (manual)
363	Round Epithelial Cells	Urine Sediment	EPIROCE	Unisex		year	0	0	1/HPF	Spot Urine Sediment	Microscopy (manual)
379	Squamous Epithelial Cells	Urine Sediment	EPISQCE	Unisex		year	0	10	1/HPF	Spot Urine Sediment	Microscopy (manual)
393	Uric Acid Crystals	Urine Sediment	CYURIAC	Unisex		year	0	0	1/HPF	Spot Urine Sediment	Microscopy (manual)
358	Bilirubin	Urine Stick Device	BILI	Unisex		year	0	0	µmol/L	Spot Urine	Urine Stick (automated evaluation; cobas u411)
359	Erythrocytes	Urine Stick Device	RBC	Unisex		year	0	0	1/µL	Spot Urine	Urine Stick (automated evaluation; cobas u411)
355	Glucose	Urine Stick Device	GLUC	Unisex		year	0	0	mmol/L	Spot Urine	Urine Stick (automated evaluation; cobas u411)
356	Ketones	Urine Stick Device	KETONES	Unisex		year	0	0	mmol/L	Spot Urine	Urine Stick (automated evaluation; cobas u411)
377	Leukocyte Esterase	Urine Stick Device	LEUKASE	Unisex		year	neg	neg		Spot Urine	Urine Stick (automated evaluation; cobas u411)
353	Nitrite	Urine Stick Device	NITRITE	Unisex		year	neg	neg		Spot Urine	Urine Stick (automated evaluation; cobas u411)
350	pH	Urine Stick Device	PH	Unisex		year	5,0	8,0		Spot Urine	Urine Stick (automated evaluation; cobas u411)
354	Protein	Urine Stick Device	PROT	Unisex		year	0	0	g/L	Spot Urine	Urine Stick (automated evaluation; cobas u411)
357	Urobilinogen	Urine Stick Device	UROBIL	Unisex		year	0	0	µmol/L	Spot Urine	Urine Stick (automated evaluation; cobas u411)

PPD PPD

PPD

PPD  
PPD

Date

PHO: Photometric; ECLIA: Elektrochemilumineszenz Immunoassay; EIA: Enzymeimmunoassay; TURB: Turbidimetry; TINIA: Turbidimetric inhibition Immunoassay; LIA: Luminescence-Immunoassay; CLIA: Chemiluminescence Immuno Assay; NEPH: Nephelometry; LFIA Lateral Flow Immunoassay

16.1.1	Planned Analyses of PK Parameter Data.....	20
16.1.2	Plasma Concentration Data.....	22
16.1.3	Estimation of Individual PK Parameters	22
17	References.....	24
18	Appendices	24

2 List of Abbreviations and Definition of Terms

AE	Adverse Event
ANOVA	Analysis of variance
BMI	Body Mass Index
CI	Confidence Interval
eCRF	Electronic Case Report Form
CSP	Clinical Study Protocol
CSR	Clinical Study Report
CV	Coefficient of variation
CV _{WR}	Within-subject coefficient of variation for the reference treatment
ECG	Electrocardiogram
GeoCV%	Geometric Coefficient of Variation
GeoMean	Geometric Mean
GMR	Geometric Mean Ratio
IAP	Integrated Analysis Plan
ICH	International Conference on Harmonization
I.e.	That is
LCI	Lower Confidence Interval Bound
LLOQ	Lower Limit of Quantification
MCAR	Missing Completely at Random
MedDRA	Medical Dictionary for Regulatory Activities
NCI-CTCAE	National Cancer Institute – Common Terminology Criteria for Adverse Events
N.R.	No result
Max	Maximum
Min	Minimum
PT	Preferred Term
PK	Pharmacokinetics
PZQ	Praziquantel
Q1	First Quartile

Q3	Third Quartile
QTcF	Corrected QT interval per Fridericia's formula
SAE	Serious Adverse Event
SEM	Standard Error of the Mean
SOC	System Organ Class
TEAE	Treatment Emergent Adverse Event
UCI	Upper Confidence Interval Bound
ULOQ	Upper Limit of Quantification

3 Modification History

Unique Identifier for Version	Date of IAP Version	Author	Changes from the Previous Version
Final 1.0	09-Jul-2020	PPD	Original Document

4 Purpose of the Integrated Analysis Plan

The purpose of this integrated analysis plan (IAP) is to document technical and detailed specifications for the final analysis of data collected for protocol MS200585_0004. Results of the analyses described in this IAP will be included in the Clinical Study Report (CSR). Additionally, the planned analyses identified in this IAP will be included in regulatory submissions or future manuscripts. Any post-hoc, or unplanned analyses performed to provide results for inclusion in the CSR but not identified in this prospective IAP will be clearly identified in the CSR.

The IAP is based upon section 9 (Statistical Considerations) of the clinical study protocol (CSP) and is prepared in compliance with ICH E9.

5 Objectives and Endpoints

Objectives	Endpoints (Outcome Measures)	IAP section
Primary		
To assess the BE of the 600 mg coated Cesol tablet versus the comparator 600 mg tablet of Biltricide at a dose of 1200 mg with regard to rac-PZQ	PK parameters C_{max} and area under the plasma concentration-time curve from time zero to last measurable concentration (AUC_{0-t}) of rac-PZQ after single dose administration	Section 16.1
Secondary		
To evaluate the safety and tolerability of the 600 mg coated Cesol tablet versus the comparator 600 mg tablet of Biltricide at a dose of 1200 mg	Occurrence of TEAEs and treatment related AEs per Qualitative Toxicity Scale Standard laboratory hematology and biochemical parameters, vital signs (body temperature, systolic and diastolic blood pressure, and pulse rate) and ECG parameters.	Section 15
To assess the BE of the 600 mg coated Cesol tablet versus the comparator 600 mg tablet of Biltricide at a dose of 1200 mg with regard to PZQ enantiomers	PK parameters C_{max} and area under the plasma concentration-time curve from time zero to last measurable concentration (AUC_{0-t}) of R-(-)-PZQ and S-(+)-PZQ after single dose administration	Section 16.1
To further characterize the PK profile of the 600 mg coated Cesol tablet versus the comparator 600 mg tablet of Biltricide at a dose of 1200 mg	PK parameters of rac-PZQ, R-(-)-PZQ and S-(+)-PZQ after single dosing: $AUC_{0-\infty}$, time to reach maximum plasma concentration (t_{max}), t_{lag} , $t_{1/2}$, λ_z , CL/f and V_z/f	Section 16.1

6 Overview of Planned Analyses

6.1 Interim Analysis

No interim analysis is planned for this study.

6.2 Final Analysis

The final, planned analyses identified in the CSP and in this IAP will be performed after the last participant has completed the last visit, i.e. end of treatment/safety follow-up visit with all trial data in-house, all data queries resolved, and the database locked.

A data review meeting will be held prior to database lock for the final analysis. In addition, no database can be locked until this IAP has been approved.

7 Changes to the Planned Analyses in the Clinical Study Protocol

There are no changes to the planned analyses in the CSP.

8 Protocol Deviations and Analysis Sets

8.1 Definition of Protocol Deviations and Analysis Sets

Important protocol deviations are protocol deviations that might significantly affect the completeness, accuracy, and/or reliability of the study data or that might significantly affect a participant's rights, safety, or well-being.

The following deviations will be identified and confirmed prior to or at the Data Review Meeting at the latest.

Important protocol deviations include

- Deviations from the inclusion and exclusion criteria
- Concomitant medication violations (see Section 6.5.2 of the protocol)
- Use of prohibited medicines (see Section 6.5.3 of the protocol)
- Participants who receive incorrect treatment or dose
- Sample processing errors that may lead to inaccurate bioanalytical results
- Vomiting or diarrhea following oral dosing (these instances will be discussed on a case-by-case basis)
- Deviation from Good Clinical Practice

- Non-compliance to study procedures or deviations from study procedures likely to affect the primary endpoints (e.g. participant develops withdrawal criteria whilst in the study but is not withdrawn)
- Deviation from study medication compliance in terms of medical conditions and/or AEs that may have interfered with drug disposition or with respect to factors likely to affect the primary endpoints

All important protocol deviations will be documented in Clinical Data Interchange Standard Consortium (CDISC) Study Data Tabulation Model (SDTM) datasets whether identified through sites monitoring or medical review.

8.2 Definition of Analysis Sets

Analysis Set	Description
Screening (SCR)	The Screening Analysis Set will include all participants, who provided informed consent, regardless of the participant’s randomization and study intervention status in the study.
Safety (SAF)	The Safety Analysis Set will include all participants who were administered any dose of any study intervention. Analyses will consider participants as treated. All safety analyses will be based on this analysis set.
PK	
The PK Analysis Set will include all participants, who receive at least one dose of study intervention, have no clinically important protocol deviations or important events affecting PK, and provide at least one measurable postdose concentration. Participants will be analyzed per the actual study intervention they received.
 
The PK population will include all participants:
 
 • Who have completed at least one study period without any relevant protocol deviations and factors likely to affect the comparability of PK results • With adequate study intervention compliance • With evaluable PK data, i.e., nonmissing values for primary endpoints in each completed study period. 
If participants received prohibited concomitant therapy or medicines, as specified in Section 6.5 of the CSP, they will be excluded from the PK population. Relevant decisions will be made before database lock. All PK analyses will be based on this analysis.

9 General Specifications for Data Analyses

Statistical analyses will be performed using the computer program package SAS[®] System for Windows[™] (Version 9.4 or later; SAS Institute, Cary, North Carolina, USA).

The results of this trial will be reported using summary tables, figures, and data listings, as appropriate. All data will be summarized by treatment sequence, period, treatment and/or scheduled time point, as appropriate. All individual data will be listed as measured in the individual participant data listing. Repeated and unscheduled measurements will be included in the listings.

For demographic, baseline and safety assessments, continuous measurements will be summarized by means of descriptive statistics (i.e. number and percentage of observations, number and percentage of missing observations, mean, standard deviation [SD], median, the first and third quartile [Q1 and Q3], minimum [Min], and maximum [Max]) and categorical data will be summarized by means of frequency tables (i.e., count and percentages), if not stated otherwise.

Percentages are based on the number of subjects dosed with each treatment in summary tables by treatment T1, T2, R1, R2, or the number of subjects in the respective analysis population for summary tables by total treatment T and R [N]. A respective footnote will be provided in the summary tables.

Mean, Median, Q1, Q3, Min, Max will have the same precision as the SDTM data (decimal places). SD will be presented with one decimal place more than the mean. For participant disposition and demographic tables the denominator will be the number of participants in the analysis set. Counts of missing observations will be included as a separate category.

If not otherwise specified, 'baseline' refers to the last scheduled measurement before administration of the first drug in each period.

If no baseline or previous to baseline evaluations per period exist then the baseline value will be treated as missing.

The following calculations and derivations, as applicable, will be used:

- Change from baseline: post-baseline visit value - baseline value
- Duration of AE (in days hh:mm) = end date and time - start date and time of the AE, if missing time for either the beginning or end then = end date – start date + 1; in case of multiple records for the same AE, the duration will be calculated over all these records
- Days hh:mm from dosing = start date and time of the event - date and time dose administration (for TEAEs), if missing time for either the dosing or event then days hh:mm from dosing = event start date – date of dose administration + 1

- Rel. Day in period of AE = start date of the event – date of First Admin in period + 1 (for AEs on or after the day of dosing)
- Rel. Day in study of AE = start date of the event – date of First Admin (for AEs before the day of dosing of the study only)

Repeated and unscheduled measurements will be included in the listings, but not used for statistical analysis or summary tables, unless the repeated measurement was performed due to unreliable values/technical reasons, e.g., clotted samples.

In this phase 1 PK study, missing observations will be assumed to be missing completely at random (MCAR). No action will be taken to handle missing data. A participant who withdraws prior to the last planned observation in a trial period will be included in the analyses up to the time of discontinuation.

The following treatment labels will be used:

Treatment Tx: x. administration of coated Cesol tablet, 2 tablets of praziquantel 600 mg per period,

Treatment Rx: x. administration of Biltricide[®], 2 tablets of praziquantel 600 mg per period

where x=1 or x=2 defines the first and second administration of test or reference product, respectively. These labels will be used in listings and summaries by first treatment and second treatment.

Treatment Total T: coated Cesol tablet, 2 tablets of praziquantel 600 mg per period,

Treatment Total R: Biltricide[®], 2 tablets of praziquantel 600 mg per period,

whereby these treatment labels will be used in summaries by total treatment.

10 Trial Participants

The subsections in this section include specifications for reporting participant disposition and treatment/trial discontinuations. Additionally, procedures for reporting protocol deviations are provided.

Considering the study objectives, it is planned to enroll 36 participants in the study to ensure inclusion of at least 32 evaluable participants for the treatment comparisons.

The participants will be randomized to one of the two treatment sequences: T1-R1-T2-R2 or R1-T1-R2-T2, where T is Test product and R is Reference product, with a washout period of at least 1 week in between.

	Period 1		Period 2		Period 3		Period 4
Sequence 1 (18 participants)	Test 1	Washout at least 7 days	Reference 1	Washout at least 7 days	Test 2	Washout at least 7 days	Reference 2
Sequence 2 (18 participants)	Reference 1		Test 1		Reference 2		Test 2

Test = coated Cesol tablet, 2 tablets of praziquantel 600 mg;
Reference = Biltricide, 2 tablets of praziquantel 600 mg.

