### 7.2 Participant Discontinuation/Withdrawal from the Study

- A participant may withdraw from the study at any time, at his own request or may be withdrawn at any time at the discretion of the Investigator for safety, behavioral, compliance, or administrative reasons.
- At the time of discontinuing from the study, if possible, a discontinuation visit will be conducted, as listed in the SoA. The SoA specifies the data to collect at study discontinuation and follow-up, and any additional evaluations that need to be completed.
- If the participant withdraws consent for future involvement in the study, any data collected up to that point may still be used, but no future data can be generated, and any biological samples collected will be destroyed.
- A participant has the right at any time to request destruction of any biological samples taken. The investigator must document this in the site study records.
- The participant may be withdrawn by the Investigator due to participation in another clinical study.

- Vomiting within the first 6 hours after study drug administration, as vomiting interferes with the PK assessments in this study.
- Not consuming the whole breakfast before drug administration.

In case of premature withdrawal from the study, the investigations scheduled for the last visit (End of Treatment/ Safety Follow-up Visit) should be performed as soon as possible, but at least 7 days after last dosing. In any case, the appropriate section in the CRF must be completed.

The WHO guideline regarding drop-outs states the following: “Sponsors should select a sufficient number of study participants to allow for possible drop-outs or withdrawals. Because replacement of participants during the study could complicate the statistical model and analysis, drop-outs generally should not be replaced.”

After discussion with the contract research organization (CRO), the nonevaluable rate (including drop-out) was set at 10%. Therefore, the number of participants to be included in the study is set to 36 to cover a minimum of 32 evaluable participants (see Section 9.2). If 5 or more participants drop out of the study before completing period 4, additional participants may be randomized to meet the required minimal number of evaluable participants (N = 32).

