10.1 Disposition of Participants and Discontinuations

This following will be presented in a summary table:

- Total number of participants screened (i.e., participants who gave informed consent)
- Number of screened participants who discontinued from the trial prior to treatment overall and grouped by the main reason for discontinuation:
 - Participant did not meet all eligibility criteria
 - Withdrew consent
 - Other (COVID-19-related and COVID-19-non-related)
- Number of randomized participants
- Number of randomized participants who did not receive treatment (as applicable)
- Number of treated participants by treatment T1, T2, R1, R2 and overall
- Number and percentage of treated participants who completed study by treatment T1, T2, R1, R2 and overall
- Number and percentage of treated participants who discontinued the study overall and number of subjects who discontinued treatment by treatment T1, T2, R1, R2, with the primary reason of discontinuation: :
 - Adverse event
 - Lost to follow-up
 - Protocol non-compliance
 - Death
 - Withdrew consent

- Other (COVID-19-related and COVID-19-non-related)

A listing of discontinued participants will be provided.

A listing of participants affected by the COVID-19 related study disruption by unique subject number identifier will also be provided.

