15.1 Adverse Events

Adverse Events will be listed by treatment T1, T2, R1, R2.

Generally, the number and percentage of participants experiencing at least one TEAE will be summarized by treatment T1, T2, R1, R2, by total T, total R and overall as well as the number of events.

A TEAE is an AE with onset after start of treatment or with onset date before the treatment start date but worsening after the treatment start date. Tables by relationship to trial drug and by severity will be generated. AEs will be coded using Medical Dictionary for Regulatory Activities (MedDRA) terminology, latest version.

If an event was reported more than once, the worst severity will be tabulated.

Incomplete TEAE-related dates will be handled as follows:

- In case the onset date is missing completely or missing partially but the onset month and year, or the onset year are equal to the start of trial treatment then the onset date will be replaced by the minimum of start of trial treatment and TEAE resolution date.
- In all other cases the missing onset day or missing onset month will be replaced by 1.
- Incomplete stop dates will be replaced by the last day of the month (if day is missing only), if not resulting in a date later than the date of the participant's death. In the latter case, the date of death will be used to impute the incomplete stop date.
- In all other cases the incomplete stop date will not be imputed.

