15.1.1 All Adverse Events

All AEs recorded during the course of the trial (i.e. assessed from signature of informed consent until the end of treatment/safety follow-up visit) will be coded according to MedDRA latest version and assigned to a SOC and PT.

TEAEs will be summarized by worst severity, using MedDRA latest version PT as event category and MedDRA primary SOC body term as Body System category. The severity of AEs will be assessed by the investigator per the Qualitative Toxicity Scale as detailed in the study protocol: mild, moderate, severe.

TEAEs related to trial treatment are those events with relationship related, or missing, or unknown.

The following will be summarized in an overview table with the number and percentage of participants (and the number of events) by treatment and overall:

- Any TEAEs
- Any trial treatment-related TEAEs
- Any serious TEAEs
- Any trial treatment-related serious TEAEs
- Any severe TEAE
- Any trial treatment-related severe TEAEs
- Any TEAEs leading to death
- Any trial treatment-related TEAEs leading to death

TEAEs will be summarized by treatment and total T, total R and overall in tables with:

- The number and percentage of participants by treatment with at least one TEAE and the number of events overall and by SOC and PT. SOC terms will be sorted alphabetically and PTs within each SOC term will be sorted by descending overall frequency.
- The number and percentage of participants by treatment with at least one non-serious TEAE and the number of non-serious TEAE applying frequency threshold of 5% according to SOC (i.e. SOC events with frequency > 5% in any arm). SOC terms will be sorted alphabetically and PTs within each SOC term will be sorted by descending overall frequency.

In addition the following tables will be provided. SOC terms will be sorted alphabetically and PTs within each SOC term will be sorted by descending frequency (based on all treatment groups combined):

- A table by severity of TEAEs with the number and percentage of participants by treatment with at least one TEAE and the number of events by SOC and PT.
- A table by relationship to trial treatment with the number and percentage of participants by treatment with at least one TEAE and the number of events by SOC and PT.

Pre-treatment AEs (AEs with onset after informed consent but before start of treatment) and TEAEs will be listed separately.

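### Adverse event percentages for total T and total R count in the denominator participants who never took that product

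*SAP*

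**What the plan says.** SAP Section 9 (General Specifications for Data Analyses) sets two denominators in one sentence. For tables by T1, T2, R1 and R2 it is the number of participants dosed with that treatment. For total T and total R it is "the number of subjects in the respective analysis population for summary tables by total treatment T and R". A table footnote is to state this.

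Safety summaries use the Safety Analysis Set. SAP Section 8.2 defines it without reference to product: "The Safety Analysis Set will include all participants who were administered any dose of any study intervention". The same entry says participants are analysed according to the treatment they actually took.

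SAP Section 15.1 says that TEAE incidence "will be summarized by treatment T1, T2, R1, R2, by total T, total R and overall as well as the number of events". Section 15.1.1 repeats the layout for the tables by system organ class and preferred term: "TEAEs will be summarized by treatment and total T, total R and overall in tables with". Neither section gives a different denominator for the totals.

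**The concern.** The sequences are T1-R1-T2-R2 and R1-T1-R2-T2, so each participant first meets his second product in period 2. Someone dosed in period 1 who leaves before the period 2 dose has taken one product only, unless a dosing error occurred (SAP Section 8.1 lists "Participants who receive incorrect treatment or dose" among the important deviations). Under the Section 9 rule he is still counted as at risk for the other product. Because events are assigned by treatment taken, he can add to that product's denominator but never to its numerator.

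One secondary objective in SAP Section 5 begins "To evaluate the safety and tolerability of the 600 mg coated Cesol tablet versus the comparator 600 mg tablet of Biltricide", and total T against total R is the natural place to read that comparison. Exits before the second dose are plausible. Protocol Sections 7.1 and 7.2 list adverse events, vomiting within 6 hours of dosing, an unfinished breakfast and noncompliance as reasons to withdraw a participant, and drug and alcohol tests are repeated before each dosing. Some of these exits would themselves be adverse events, so they need not balance between sequences.

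**Working it through.** **Inputs from the documents.** Planned enrolment is 36, with at least 32 evaluable and a nonevaluable rate of 10% including drop-out (Protocol Section 7.2). The plan's own figure reproduces: 32/(1 − 0.10) = 35.56, rounded up to 36, or 18 per sequence.

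**Assumptions.** The Safety Analysis Set is N = 36. The documents give neither the number of exits before period 2 nor the TEAE rates, so the values below are illustrative.

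**One product.** Let k be the number of participants who leave before period 2 without having received the product, and x the number with a TEAE on it.

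- Printed percentage: x/N
- Percentage among those exposed: x/(N − k)
- Printed divided by exposed: (N − k)/N, a relative understatement of k/N

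| k | Dosed with product | Relative understatement | True 25.0% prints as |
|---|---|---|---|
| 0 | 36 | 0% | 25.0% |
| 1 | 35 | 1/36 = 2.8% | 25 × 35/36 = 24.3% |
| 2 | 34 | 2/36 = 5.6% | 25 × 34/36 = 23.6% |
| 4 | 32 | 4/36 = 11.1% | 25 × 32/36 = 22.2% |

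**Both products.** Let a be the early losses in T1-R1-T2-R2 (no R taken) and b those in R1-T1-R2-T2 (no T taken). Then 36 − a received R and 36 − b received T. The printed R:T ratio is the true ratio times (36 − a)/(36 − b). With assumed true rates of 30% for R and 20% for T, the true difference is 10.0 points. Differences are taken before rounding.

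| a / b | R printed | T printed | Difference (points) | Ratio factor |
|---|---|---|---|---|
| 1 / 1 | 29.17% | 19.44% | 9.72 | 1.000 |
| 2 / 2 | 28.33% | 18.89% | 9.44 | 1.000 |
| 1 / 0 | 29.17% | 20.00% | 9.17 | 35/36 = 0.972 |
| 2 / 0 | 28.33% | 20.00% | 8.33 | 34/36 = 0.944 |
| 0 / 1 | 30.00% | 19.44% | 10.56 | 36/35 = 1.029 |
| 0 / 2 | 30.00% | 18.89% | 11.11 | 36/34 = 1.059 |

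Equal losses leave the ratio intact but lower both rates and shrink the difference. Unequal losses move the comparison in either direction.

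**Consistency within one table.** Suppose one participant leaves before R1, eight have a TEAE on R1, and nobody has a first one on R2. R1 prints 8/35 = 22.9% and total R prints 8/36 = 22.2%, so the pooled column falls below one of its components. With one new case on R2 the order is normal: 9/36 = 25.0% as planned, against 9/35 = 25.7% among those dosed.

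**The case against.** **Another reading of the text.** The word respective, the as-treated rule, and the Section 9 statement that a withdrawn participant is included up to discontinuation might together be taken to mean that only those exposed to a product count for it. This does not hold. The sentence sets its wording for the totals against the number dosed, and two rules would be pointless if they meant the same. The Safety Analysis Set is not defined by product, and the statement on withdrawal concerns missing data and sets no denominator. If the sponsor did intend those exposed, the sentence still needs rewording.

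**The reader can recover the right figure.** This stands. The T1 and R1 columns use the number dosed, event counts are printed, and the disposition table gives the "Number of treated participants by treatment T1, T2, R1, R2 and overall". The footnote will disclose the denominator, though it will not change the percentage.

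**The effect may be nil, and large cases are strained.** This stands too. The 10% covers all reasons over four periods, about 4 of 36 (0.10 × 36 = 3.6). Four early losses in one sequence would use the whole allowance in one interval. Five would reach the point where the protocol says "If 5 or more participants drop out of the study before completing period 4, additional participants may be randomized", and replacement would raise N: 5/36 = 13.9% becomes, for example, 5/37 = 13.5%. The range of zero to two losses is the sensible one to carry forward.

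**No TEAE ratio or difference is planned.** Correct. The second table above shows only what a reader comparing the two columns would infer.

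**Conclusion.** The point holds as the SAP is worded. After any exit between the period 1 and period 2 doses, the total column for the product not received prints an incidence that is too low by k/N. With an assumed N of 36 that is 2.8% relative for one loss and 5.6% for two, which is 0.7 and 1.4 percentage points at an assumed incidence of 25%. If all four losses allowed for by the 10% rate fell in T1-R1-T2-R2 before period 2, equal true rates of 25% would print as 25.0% for T and 22.2% for R. The documents give no likelihood for any of these patterns, and with no such exit the error is zero. It is a minor matter: descriptive secondary safety tables only, with no bearing on the bioequivalence analysis. It is worth correcting because the rule gives the wrong answer in the one comparison those columns exist to show.

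**What to change.** In SAP Section 9, replace the rule for the totals with:

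> Percentages for total T and total R are based on the number of Safety Analysis Set participants who received at least one dose of T or R, respectively. Percentages in the overall column are based on the full Safety Analysis Set.

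Align the planned footnote with this. Barring dosing errors, the new denominators equal the T1 and R1 treated counts already tabulated under SAP Section 10.1. The cost is one sentence, a small change to how the total columns are programmed, and the footnote text. No extra data are needed, and the tables are unchanged if everyone dosed in period 1 is also dosed in period 2.
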